6.0 Study Agent and Intervention Description

Options

Capsules: 40 mg/1 .5 mg or 80 mg/3 mg CBD:THC per capsule (Gelatin capsules: Apothecon).

Interventions

All patients and marijuana naive (no marijuana use within the last 30 days) will receive 40/1.5 mg CBD:THC three times daily. Marijuana tolerant patients (Marijuana use currently or within the last 30 days) will receive 80 mg/3 mg CBD: THC three times daily.

Patients who experience three scheduled opioid dosage increases while receiving the 40 mg/1 .5 mg regimen will have an increase to the 80 mg/3 mg dosage three times daily for the remainder of the study.

Security/Records

All study drugs will be secured abiding by federal and state regulations for storage of Scheduled substances.

Running inventory will be maintained for all study product. The pharmacy staff will record receipt and dispensing of study product, and maintain adequate supply and availability for the study population in accordance with all federal narcotic regulations.

Storage of Scheduled study product will be accessible to pharmacy personnel and clinical staff caring for the patient, in accordance with the hospital's policies and procedures and in accordance with both state and federal storage requirements.

7.0 Study Schedule:

Patients must have, at minimum, a 3-day life expectancy

SCREENING

ENROLLMENT

DOSING -5 Ongoing Assessment of Patient Progress and Safety

DATA COLLECTION

DATA ANALYSIS

Adverse/Serious Adverse Events: dysphoria, extreme anxiety/panic attack, paranoia, psychosis, ataxia, impaired motor coordination, any condition that would typically not be associated with the patients admitting diagnosis or normal course of illness.

Adverse reactions will be immediately documented on the Connecticut Hospice Adverse Drug Reaction Form and evaluated by the PI and clinical investigation team. The research team will

determine whether changes to the study protocol, including discontinuation of the study, are warranted.

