4.0 Study Design and Methodology

Design

This will be an open-label study. Patients will choose to participate in a Marijuana adjuvant treatment group, receiving marijuana in combination with standard opioid therapy.

The goal is to enroll at least 66 Hospice patients in the study.
Methodology

Patients will be notified of the study's existence through communication with the study's investigation team at time of admission. Patients will be screened for study eligibility—see section 6.0 for study eligibility factors—and if the patient is both eligible and interested in participating, the sub-investigator will discuss and review the informed consent form with the patient and obtain their signature; the patient will then have a consultation with a prescribing physician; and, if the physician has determined that medical marijuana is a viable option for that patient, registration with the Connecticut Medical Marijuana program will begin. For patients who have already been prescribed both marijuana and opioid medication upon admission to Hospice, signing the consent form will complete study enrollment.

Patients' initial opioid dose, dosing schedule and numeric pain score will be recorded. For the duration of the study (at least five days) changes in opioid doses and numeric pain scores will be tracked daily.

Marijuana will be administered to the patient via oral route three times daily for at least five days. Patients will receive CBD:THC product provided by NIDA.

On admission to the study, a modified Edmonton Symptom assessment scale to quantify baseline appetite, depression, nausea, vomiting, overall well-being, and anxiety.

Data Tracking: Primary objective tracking will include average numeric pain scores and number of opioid dosage increases and average daily opioid amount (mg equivalents of morphine).

Secondary objectives include Weight, Appetite, N/V, O2 Saturation, Self-reported data points from the modified Edmonton Assessment Scale.

Data Tracking Intervals: Primary objective tracking of pain will be daily every 4 hours (twice per shift). Secondary objective tracking as follows: Weight daily, Appetite every 8 hours (every shift), N/V, O2 saturation as reported by clinician documentation, Edmonton scale results three times weekly.

Analysis

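### Section 6.0 makes doubling of CBD/THC mandatory after three scheduled opioid increases, with no tolerability condition on taking or keeping the higher dose

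*Combined protocol and SAP*

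**What the plan says.** Section 6.0 (Interventions) sets two dose levels, each given three times daily. Patients with no marijuana use in the last 30 days start on 40 mg CBD/1.5 mg THC. Those with current or recent use start on 80 mg/3 mg. One rule moves a patient between levels: "Patients who experience three scheduled opioid dosage increases while receiving the 40 mg/1 .5 mg regimen will have an increase". The rest of that sentence gives the new dose and how long it lasts: "to the 80 mg/3 mg dosage three times daily for the remainder of the study".

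Section 7.0 holds most of the safety text. The schedule carries the line "DOSING -5 Ongoing Assessment of Patient Progress and Safety". The events of interest begin "Adverse/Serious Adverse Events: dysphoria, extreme anxiety/panic attack, paranoia, psychosis, ataxia, impaired motor coordination" and end with a catch-all for conditions not typical of the admitting diagnosis or the normal course of illness. On handling, "Adverse reactions will be immediately documented on the Connecticut Hospice Adverse Drug Reaction Form and evaluated by the PI and clinical investigation team". Those running the study are then to "determine whether changes to the study protocol, including discontinuation of the study, are warranted".

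Section 4.0 gives the planned course: "Marijuana will be administered to the patient via oral route three times daily for at least five days". It also places a physician's judgement before treatment starts: "if the physician has determined that medical marijuana is a viable option for that patient, registration with the Connecticut Medical Marijuana program will begin". Section 13.0 adds that a nurse is present at dosing and that any suspension of the study is reported to the IRB.

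**The concern.** The escalation sentence is an instruction, and its only input is an efficacy signal: rising opioid need. The same document says in section 2.0 that higher THC doses have been associated with psychosis-like symptoms and with motor and cognitive impairment, and section 7.0 lists events of that kind. The rule nevertheless raises THC without asking whether any of them is present.

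The timing adds to this. The step comes just after the scheduled opioid dose has risen three times. Section 2.0 lists sedation and respiratory depression among opioid side effects, and cites reasoning that marijuana may slow opioid metabolism or raise plasma opioid levels. A tolerability check is most useful at that moment.

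The patient at risk is one who is already reacting at 40/1.5 mg. A clinician who sensibly withheld the increase would be departing from a written requirement, and different clinicians could handle similar patients differently.

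**Working it through.** **Inputs.** From section 6.0: 40 mg CBD/1.5 mg THC and 80 mg CBD/3 mg THC, each three times daily. From section 2.0: opioid doses are typically adjusted in 25% increments.

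**1. Size of the step.** Daily dose = 3 × dose per administration.

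| | Before | After | Ratio |
|---|---|---|---|
| THC (mg/day) | 3 × 1.5 = 4.5 | 3 × 3 = 9 | 2.0 |
| CBD (mg/day) | 3 × 40 = 120 | 3 × 80 = 240 | 2.0 |

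Each full day at the higher level adds 4.5 mg THC and 120 mg CBD. CBD:THC is 40/1.5 = 80/3 = 26.7 at both levels, so the step does not increase CBD relative to THC.

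**2. Opioid dose when the step is taken (illustrative).** Assume that each of the three increases is the typical 25%. If they compound, the scheduled opioid dose is 1.25³ = 1.95 times its starting level. If each is 25% of the starting dose, it is 1 + 3 × 0.25 = 1.75 times. The protocol does not fix the size of these increases, so 1.75 to 1.95 is a range under an assumption and not a protocol figure.

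**3. Does any other text condition the step?**

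- Section 6.0, escalation sentence: one trigger, a mandatory result and a duration to the end of the study. It contains no condition and no step back.
- Section 7.0, schedule line: safety is assessed throughout dosing, but the line is not linked to the escalation decision.
- Section 7.0, reaction handling: each reaction is recorded and evaluated. The outcomes named next are changes to the protocol and discontinuation of the study. Even if the latter is read loosely to include one patient coming off study, it neither conditions the increase nor provides for a return to 40/1.5 mg.
- Section 4.0, physician's judgement: made before registration with the state program and not repeated at escalation.
- Section 5.0, exclusion of agitated or combative patients: applies at entry.
- Section 13.0: nurse presence and study-level suspension. Neither concerns the step.

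None of these qualifies the escalation sentence.

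**4. How many patients?** This cannot be computed. A patient must start on 40/1.5 mg, have three scheduled (not as-needed) opioid increases, and have an unresolved reaction at that point. The documents give no rate for the second or third event and no split between the two starting doses.

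**The case against.** The strongest case against is that the rule sits inside a system that would catch the problem. Participants are inpatients, nurses attend dosing, safety is assessed throughout, and each reaction goes at once to the PI and team. Immediate evaluation serves little purpose if it cannot affect that patient's treatment, so a clinician would very likely withhold the increase. The harm needs several events to coincide, in a hospice where section 5.0 gives an average stay of twelve days. No figure in the documents shows that 9 mg THC a day is harmful: section 2.0 gives no milligram threshold for the effects it describes and says CBD appears to block them in part. The higher level is also a planned starting dose.

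Most of this stands, and it limits the size of the point. It does not change what the sentence requires. The 80/3 mg starting dose is reserved for patients with recent marijuana use, whereas the rule applies to patients started at the lower level.

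A reader might go further and infer that the protocol allows no hold, reduction or stop for any individual patient at either dose level, or that the five-day course compels dosing through toxicity. The documents do not support that. Evaluation by the PI and ongoing safety assessment leave room for ordinary clinical action. Section 7.0 accepts a three-day life expectancy, so five days is better read as a planned course. The section numbers also run from 7.0 straight to 10.0, and the consent pages are not part of the text reviewed, so withdrawal or stopping wording may exist elsewhere. The point is therefore confined to the escalation sentence.

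**Conclusion.** The point holds for the section 6.0 escalation rule. As written, it requires an exact doubling, from 4.5 to 9 mg THC and from 120 to 240 mg CBD a day, on opioid count alone, and it sets the higher dose for the rest of the study. Nothing else in the text reviewed makes taking or keeping that step depend on tolerability. Followed exactly, it would double the dose in a patient with an ongoing reaction that section 7.0 lists.

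This is a modest safety correction. The number affected is unknown and probably small, and clinical judgement would probably intervene. The conclusion rests on the literal wording of the rule and on the sections available. It does not rest on any claim that 80/3 mg is unsafe in itself, and it does not extend to a general absence of patient-level dose actions.

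**What to change.** Amend the escalation sentence in section 6.0 in two places.

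1. **Condition on the step.** After three scheduled opioid increases on 40/1.5 mg, the dose rises to 80/3 mg three times daily only if the PI or clinical investigation team finds no ongoing section 7.0 reaction, and no clinically significant sedation or respiratory depression, judged possibly related to study drug or to its combination with opioids. Sedation and respiratory depression need naming because the section 7.0 list does not name them, and its catch-all might not be read to include recognised opioid effects.
2. **Condition on staying.** Qualify the closing phrase on duration so that the higher dose continues to the end of the study if tolerated, with return to 40/1.5 mg or stopping at the PI's judgement.

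Record each such decision, with its date, on the existing Adverse Drug Reaction Form. The record would also show when a patient's dose departed from the rule, which helps when reading the pain and opioid results.

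The cost is one amended sentence, one dated entry on a form already in use, and a relatedness judgement by the PI or team. Slightly fewer patients would escalate or stay escalated. The opioid trigger, the endpoints and the target of 66 patients are unchanged.

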2.0 Background and Significance

The Connecticut Hospice, Inc., the first Hospice who served for four decades in the United States, recently received The Joint Commission 's first advanced palliative hospital certification without recommendations for improvement, embarks on a new study.

Hospice care (Johnson-Hurzeler 1998) involves managing symptoms and quality of life for patients whose life expectancy is less than six months. (Kruse 2013) A study involving 100 hospice inpatients revealed high incidence of many symptoms, including chronic pain (62% of patients), anorexia (58%), constipation (52%), nausea (37%), vomiting (24%), sleep issues (22%), and anxiety (19%). (Potter 2003) The majority of hospice patients are prescribed opioids for pain control. The typical process involves administering a certain dosage of opioids and, depending upon pain relief and side effects, the dosage (in mgs) may be adjusted accordingly in increments of 25%. Common side effects of opioid medications include constipation, nausea, sedation, respiratory depression, dependence, and death. (Bruehl 2014)

In studies to date, marijuana has shown promise as an adjunctive medication for patients who require opioids for pain management. (Karst 2009) An Australian study—POINT (Pain and Opioids in Treatment)—collected reports from 1,514 patients on the efficacy of marijuana in combination with opioids for management of pain from a diverse range of causes. (Degenhardt 2015) In general, patients reported that the combination of marijuana and opioids was more effective for pain relief than opioids alone. (Degenhardt 2015) Another study, which included 21 patients suffering from chronic pain, found increased efficacy in pain control with the addition of marijuana to opioid regimens; investigators concluded that addition of marijuana to opioid regimens may result in a lowered effective dose of opioids. (Abrams 2011) In the same study, investigators reasoned that marijuana facilitates the activities of opioids either by slowing opioid

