metabolism or by increasing plasma opioid levels. (Abrams 2011) Marijuana may also facilitate the pain-relieving effects of opioid medications by acting upon opioid receptors. (Cichewicz 2004; Abrams 2011) Animal studies have shown the possibility of direct interaction between cannabinoid and opioid receptors. (Bushlin 2010) In studies, marijuana has been shown to reduce pain associated with multiple sclerosis, HIV, chronic neuropathic pain, rheumatoid arthritis, and acute pancreatitis. (Fine 2013) Surveys of medical marijuana have shown that the drug can improve pain and control insomnia with minimal side effects in some patients. (Wilsey 2008) Marijuana is also known to help mitigate nausea and vomiting. (Sharkey 2014) Dronabinol, a pill which is chemically identical to THC, was approved in 1992 by the FDA as an appetite stimulant in AIDS patients. (Grant 2005) The latter may indicate the use of marijuana for hospice patients experiencing anorexia.

Most studies of the medical benefits of marijuana so far have included fewer than 200 patients. Federal restrictions make it difficult for the research to advance. Marijuana is currently characterized by the Federal Government as a Schedule-I controlled substance, meaning that according to federal law, "(A) The drug or other substance has a high potential for abuse. (B) The drug or other substance has no currently accepted medical use in treatment in the United States. (C) There is a lack of accepted safety for use of the drug or other substance under medical supervision." (21 U.S. Code *812) The DEA and FDA have yet to grant their approval for largescale studies of the medical applications of marijuana; however, in 2014, the FDA vowed to reexamine the scheduling of marijuana so that more large-scale research could perhaps be conducted. (Ferner 2014)

In 2012, Connecticut lawmakers passed a law allowing for the palliative use of marijuana. The law enables doctors to prescribe marijuana (i.e. dried leaves) and its derivatives (i.e. oils, waxes, edibles, transdermal, and sublingual preparations) to patients suffering from specific conditions.

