Under Connecticut state law "Debilitating Medical Condition" includes Cancer or terminal illness requiring end-of-life care. This study specifically will enroll cancer and non-cancer patients as a primary diagnosis suffering from pain and having a terminal illness (defined as having less than 6 months to live) requiring end of life care. Table-I .(pg. 8) Originally published in Cancer Therapeutics in 1998, and revised in 2016, includes the specific inclusion diagnoses for this study). Under the international classification of disease (ICD-10), these diagnoses are categorized in The Connecticut Hospice-Hospital database for fiscal year 2016, representing patients that have been referred and admitted.

Table 1.

The Connecticut Hospice, Inc.

SUMMARY GUIDELINES FOR INITIATION OF ADVANCED CARE

(OVER FOR REFERRAL INFORMATION)

Authored by: [name].

[name], MPH, HA

Limited response to additional therapy expected and not durable.

First-line salvage therapies have failed. Less than 30% response to second-line or other therapy expected and not durable.

Dementia beyond Stage 7 of the Functional Assessment Staging Scale for Alzheimer's Disease or multi-symptoms present and declining functional status (Karnofsky and when there is partial or total dependence in ADLs.)

Progressive nerve degeneration with resultant partial/total paresis or paralysis of extremities and muscles of respiration. Optimal therapy reached. (i.e. no further response to therapies expected). With major symptoms present and declining functional status (Karnofsky 50% and when there is partial or total dependence in ADLs).

Massive CVA with no rehabilitation potential; patient unable to eat. Optimal therapy reached (i.e. no further response to therapies expected, with major symptoms present and declining functional status (Karnofsky and when there is partial or total dependence in ADLs).

Congenital defects, complication of infections, or trauma based upon individual case review.

Long-standing history of congestive heart failure or multiple MI. Class IV NY Heart Association Symptoms and ejection fraction. No further responses expected to medical therapy and no options for CABG, grafting, angioplasty, pacemaker, or transplant. Any one of the following: dyspnea, angina, orthopnea, edema. Any two of the following: Karnofsky <50%, minimal activity tolerance, dependence on 20 or more ADLs.

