Degradation of PFTs: FEV1 after bronchodilator <30 % of predicted, decrease in FEV1 on yearly serial testing of >40ml/year. Cor pulmonale, Hypoxemia, significant CO₂ retention as measured by ABGs. Optimal therapy reached with multiple bronchodilators and steroid dependence with dyspnea (of any kind) and O₂ dependence. Declining functional status including Karnofsky <50%, chair-bound, minimal activity tolerance, and dependence on 2 or more ADLs.

Worsening LFTs and documented evidence of disease (utilizing abdominal ultrasound, CT, HIDA Scan, Cholangiography, ERCP or any appropriate diagnostic imaging demonstrating biliary obstruction, hepatic vein occlusion, hepatic artery thrombosis, hepatocellular dysfunction. No expectation of success from medical management and/or surgical intervention. Presence of any one major symptom and declining function status (Karnofsky <50% and dependence in 2 or more ADLs).

10. Decision made to stop dialysis with one of the following conditions: chronic dialysis necessary to sustain life, disease progression despite interventions, intolerable associated medical complications of non-renal disease. In addition, at least one of the following: peripheral vascular disease degradation, hypotension, dementia, depression, resistance to dialysis Rx; and, declining functional status.

11. CD4<50 with concurrent ongoing major infections, and the presence of at least one of the following: lymphoma, Kaposi's Sarcoma, PMH, HIV encephalopathy, HIV wasting syndrome. Progression of disease on antiretroviral therapy and the presence of major symptoms with declining function status.

Important Note on these Guidelines: The footnotes above are an integral part of these guidelines. They must be used in conjunction with the matrix at the left. Cancer Therapeutics: May/June 1998*Vol 1, No.2

Disease Category	Initial Diagnosis	Refer to Advanced Care upon		
		Recurrence	Progression	Critical Clinical Decision
Cancer				
Brain/CNS Tumor				
Breast				
Colorectal				
Esophagus				
Gall Bladder				
Head & Neck				
Leukemia				
Liver				
Lung				
Lung - inoperable				
Melanoma				
Ovarian - inoperable				
Ovarian/GYN				
Pancreatic				
Prostate/GU				
Renal				
Sarcoma				
Stomach Non-Hodgkin's Lymphoma				
End-Stage Diseases				
Neurological: Alzheimers Disease				
ALS		4		
CVA			5	
MS			4	
Congenital, Infectious, or Traumatic Disability				
Heart Failure		7		
Lung-COPD		8		
Liver Failure/ Cirrhosis		9		
Kidney Failure			10	
AIDS		11		

Options:
In
R

P

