Following the data collection phase, investigators will calculate average numeric pain scores, average number of increases in opioid dosage and average daily opioid amount (mg equivalents of morphine). Analysis will examine whether the addition of CBD/THC with opioid therapy had

a stabilizing effect or improvement in pain management (lower average numeric pain scores, few dosage increases, lower opioid doses and subsequently less opioid therapy needed)

Additionally calculations will include results of changes in weight, calculation of average changes in O2 saturation, and average changes in Edmonton-Scale scores for secondary data collection points.

Patient Selection to Ensure Validity

The study will enroll patients with a primary diagnosis (Table 1) of cancer and non-cancer with associated pain considered to have a terminal illness requiring end of life care, utilizing routine or as needed opioid therapy for pain.

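### The adverse-event definition names neither sedation nor respiratory depression, and its catch-all allows both to be treated as normal course and left out of the adverse-event record

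*Combined protocol and SAP*

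**What the plan says.** Section 7.0 sets out what qualifies as an adverse or serious adverse event. It names six events, all psychiatric or motor, and then admits "any condition that would typically not be associated with the patients admitting diagnosis or normal course of illness". Reactions are documented on the hospice's Adverse Drug Reaction Form and evaluated by the PI and clinical investigation team, who decide whether the protocol should change or the study stop.

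Section 2.0 describes the risks of the background treatment: "Common side effects of opioid medications include constipation, nausea, sedation, respiratory depression, dependence, and death". It also reports reasoning from an earlier study that marijuana may assist opioids by slowing their metabolism or "by increasing plasma opioid levels". Section 5.0 makes opioid use, scheduled or as needed, a condition of entry.

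Table 1 gives the qualifying diagnoses. Its note on nerve degeneration includes "paralysis of extremities and muscles of respiration". Its note on lung disease includes "Cor pulmonale, Hypoxemia" and significant CO2 retention.

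Section 4.0 takes oxygen saturation from clinician documentation, with no stated interval, and plans "calculation of average changes in O2 saturation". The Edmonton items listed in sections 4.0 and 10.0 are appetite, nausea, vomiting, depression, anxiety and well-being. Section 10.0 lists no adverse-event count or rate.

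**The concern.** The two opioid effects most relevant to adding a second centrally acting drug are foreseen in the background but missing from the event list. They can enter the record only through the catch-all, and that clause asks whether a condition is typical of the patient's diagnosis or illness. It does not ask whether the study drug could have caused or worsened it.

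In a hospice population, drowsiness and failing respiration can often be called typical. There is no comparator arm to show whether they occur more often than expected, and the supplied text gives no attribution rule or severity grading. Two teams could apply the definition in good faith and record different events.

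What is at stake is the input to the safety review. An episode put down to the illness need not be documented as an adverse event, so it may not come before the PI and team in that form. Any later tabulation of adverse events would inherit the same selection.

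**Working it through.** The plan gives no figure on this point to reproduce. The check is mainly a comparison of passages, with two small calculations.

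**1. Are the events named?** Section 7.0 names six events. Neither sedation nor respiratory depression is among them.

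**2. Are they foreseeable?** Yes, on the protocol's own text. Both appear in the section 2.0 list of opioid side effects, every participant takes opioids (section 5.0), and section 2.0 reports a proposed interaction that would raise opioid exposure. That mechanism is presented as investigators' reasoning, not as an established effect.

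**3. Does the catch-all bring them in?** Not reliably, and the support differs between the two events.
- *Respiratory depression:* Table 1 describes eligible patients with paralysed respiratory muscles, hypoxemia or CO2 retention. For them, respiratory compromise is typical of the admitting diagnosis, so the clause as written can exclude it. The share of participants with these diagnoses is not given.
- *Sedation:* none of these Table 1 notes bears on it. That it could be called normal course is an inference from a terminally ill population. On the other side, section 5.0 requires patients to be alert at entry, so marked new sedation would be a visible change.

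**4. Does other planned data collection fill the gap?**
- *Sedation:* no listed Edmonton item covers it, and the supplied text shows no other planned measure.
- *Respiratory depression:* oxygen saturation is a partial proxy, but it is unscheduled and summarised as an average change. An average says little about single events. Assume all 66 target patients are measured, one falls by d points and the rest do not change. The mean then moves by d/66:
  - d = 5 (assumed): 5/66 = 0.08 points
  - d = 10 (assumed): 10/66 = 0.15 points
  - d = 15 (assumed): 15/66 = 0.23 points

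**5. What could a complete record show at this size?** With n = 66 and no events, the exact (Clopper-Pearson) two-sided 95% upper limit is 1 − 0.025^(1/66) = 0.0544, or 5.4%. That reading is valid only if every case is recorded, which the present definition does not secure.

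**6. How large is the under-recording?** This cannot be derived. The documents give no event rate and nothing on how staff would classify these episodes.

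**The case against.** The strongest reply is that drug-induced sedation or respiratory depression is by nature not the normal course of the illness, so a plain reading of the catch-all already covers it. There are also practical protections. Adverse reactions go on a dedicated form, nurses are present at dosing, pain is checked every 4 hours, safety is assessed on an ongoing basis, and the monitoring paragraph in section 13.0 promises continuing review of the study. Oxygen saturation and heart rate are examined whatever the attribution. The form itself was not available and may already list these events or carry a causality field. The supplied section numbering runs from 7.0 to 10.0, so further safety text cannot be ruled out.

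Part of this stands. The wording permits omission and does not compel it, and staff would probably notice a marked episode. But noticing an event does not make it qualify under section 7.0. The clause turns on what is typical and not on cause, and cause is the hardest thing to judge at the bedside in this population. If the form does contain the missing items, section 7.0 can say so.

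A reader might also infer that the plan's adverse-event count will be biased by some stated amount. The documents do not support that: section 7.0 defines events for documentation and review, and section 10.0 plans no count. Nor do they support the inference that these events would go unobserved or that safety is unmonitored.

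**Conclusion.** The point holds in a limited form. Two foreseeable opioid effects are absent from the named events, and the catch-all lets them be classed as illness and left out of the record that the PI and team evaluate. The textual support is direct for respiratory depression and inferential for sedation. The gap in other planned data is wider for sedation, which has no listed measure, than for respiratory depression, which has unscheduled oxygen saturation.

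The size of any under-recording is unknown. The conclusion rests on the supplied text alone and would weaken if the Adverse Drug Reaction Form or a section not supplied already names these events. It does not touch the pain or opioid-use objectives. It is worth acting on because the study is an exploratory Phase I pilot of a drug combination, and the change is cheap.

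**What to change.** **Section 7.0.** Add wording to this effect: *Sedation and respiratory depression are adverse events in this study and are recorded whenever observed, regardless of presumed cause. Attribution is entered afterwards in a separate field, using categories defined in advance, and does not affect whether the event is recorded.* The investigators should set working definitions of both events before enrolment.

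**Section 10.0.** Report the number and proportion of patients with each event, with exact 95% confidence intervals. Describe these as total rates under combined treatment and not as marijuana-attributable rates, because there is no comparator.

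**If desaturation is also counted.** Use a threshold fixed in advance by the investigators and state how many patients had oxygen saturation measured. It is recorded only as clinicians document it, so the count depends on who was measured. Show it beside the average change.

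**Cost.** A few lines in two sections, a short list of attribution categories, and more form entries, many of them due to the underlying illness. The separate field keeps those entries distinguishable but cannot prove cause. Sedation can be noted at the existing pain checks (24 h / 4 h = 6 a day), so no new assessment time is needed. Scheduled oxygen saturation readings would be an additional burden, and this fix does not require them.
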